8.3.5.7. Serology

Anti-Streptolysin antibody, anti-phospholipid antibody, hepatitis, and HIV tests will be performed at a central laboratory (see Table 1). Hepatitis and HIV tests will be conducted during the screening period. If participants are positive for active disease, they should not be enrolled per exclusion criteria. Note: HIV screening test is optional for participants enrolled in the United States, but participants with known HIV infection enrolled in the United States will be excluded.

Table 5: Required Laboratory Analytes

Serum Chemistries	Hematology ^{a,b}	Urinalysis With Microscopic Examination	Screening Serology	Coagulation	
Albumin	CBC, including:	Color and appearance	Hepatitis B surface antigen	D-Dimer	
Alkaline phosphatase	Hemoglobin	pH and specific gravity	Hepatitis B surface antibody		
ALT	Hematocrit	Bilirubin	Hepatitis B core antibody		
AST	Platelet count	Glucose	Hepatitis C virus antibody		
Bicarbonate	RBC count	Ketones	Hepatitis C virus-RNA (only		
Blood urea nitrogen	WBC count	Leukocytes	performed if antibody positive)		
Calcium	De teum	Nitrite	HIV antibody		
Chloride	Differential count, including:	Occult blood	Anti-streptolysin antibody		
Creatinine	Basophils	Protein	Anti-phospholipid antibody		
Ferritin (screening visit and repeat at	Eosinophils	Urobilinogen			
Week 6 if participant has ongoing	Lymphocytes		Hemolysis Markers ^b		
transfusion requirements)	Monocytes	Haptoglobin (will be measured in	serum chemistry panel)		
Folic acid (screening visit)	Neutrophils	LDH (will be measured in serum chemistry panel)			
Glucose	Neutropinis	Reticulocyte count (will be measured in hematology panel)			
Haptoglobin	Absolute values must be	Hemoglobin (will be measured in hematology panel)			
Iron (screening visit and repeat at	provided for WBC differential				
Week 6 if participant has ongoing transfusion requirements)	laboratory results:	Total bilirubin ^c (will be measured	DAT and Cold Agglutinin Test		
LDH	Lymphocytes	DAT for IgG and C3d*			
Phosphate	Neutrophils	Cold agglutinin levels*			
Potassium		* Baseline and EOT			
Sodium		Other Assessments			
Total bilirubin ^c		Urinalysis			
Total protein		FSH			
Total iron-binding capacity		Urine pregnancy test (at site)			
(screening visit and repeat at Week 6		Serum pregnancy test			
if participant has ongoing transfusion	Complement assessment (CH50, C3, and C4)*				
requirements)		* Baseline and EOT			
Uric acid		Vitamin B12 (screening visit)			

Note: Additional tests may be required, as agreed upon by the investigator and sponsor, based on emerging safety data.

^a Hematology parameters will be managed in real-time by local laboratory assessments.

b Hematology panels and hemolysis markers need to be performed in accordance with the standard of care at each investigational site for the participant's condition and monitoring at the investigator's discretion.

^c If total bilirubin is elevated above ULN, direct/indirect bilirubin will be measured.

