f Serology includes HIV, hepatitis, anti-Streptolysin antibody, and anti-phospholipid antibody tests.

g For women of nonchildbearing potential only (ie, surgically sterile with a hysterectomy and/or bilateral oophorectomy OR postmenopausal, defined by last menstrual period > 12 months before screening and confirmed by FSH).

^h For women of childbearing potential only.

¹ Ferritin, iron, and total iron-binding capacity will be tested at screening for all participants and at Week 6 if the participant has ongoing transfusions requirements during the study.

Single ECG. At screening, in the event that a single QTcF is > 470 milliseconds for males or > 480 milliseconds for females, triplicate ECG measurements may be performed.

k Hemoglobin, haptoglobin, LDH, reticulocyte count, total bilirubin and direct/indirect bilirubin are hemolytic markers will be measured. During follow-up, these hemolytic markers should be assessed if a participant becomes symptomatic or starts new treatment; relevant biomarkers should also be included.

Plasma for PK analysis will be collected predose and 1, 2, and 4 hours postdose at Weeks 2 and 8. Predose PK will be collected at Weeks 1 and 12.

Table 2: Schedule of Assessments for the Extension Period

		Extension Period			Follow-Up	
Procedure	Protocol Section	At Least Every 8-12 Weeks in Clinic	EOT Extension Period	Month 1 + 5 days	Month 2 ± 5 days	Month 3 ± 5 days (EOS)
Prior/concomitant medications	8.1.5	X	X	X	X	X
Study drug dispensing	6.1	X				
Study drug accountability and assess compliance	6.5	X	X			
AE assessment	8.3.1	X	X	X	X	X
Prophylactic treatment for PJP	6.7.1.1	X	X	X	X	X
Hematology ^{a,b}	8.2.1	X	X	X	X	X
Hemolysis markers ^a	8.2.1	X	X	X	X	X
Serum chemistries ^a	8.3.5.1	X				

^a Performed at each site as per the standard of care for participant's condition and monitoring at the investigator's discretion. Frequency to be determined by the investigator if it is necessary to monitor any other ongoing clinical condition.

^b Hematology panel will be performed at local laboratory.

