3. OBJECTIVES AND ENDPOINTS

Objectives	Endpoints					
Primary						
To evaluate the efficacy of INCB050465 in the treatment of participants with AIHA.	• Proportion of participants attaining a CR (defined as hemoglobin >12 g/dL not attributed to transfusion effect* and the normalization of hemolytic markers) at any visit from Week 6 to Week 12.					
	 Proportion of participants attaining a PR (defined as hemoglobin 10-12 g/dL or at least ≥ 2 g/dL increase from baseline not attributed to transfusion effect and the normalization of hemolytic markers) at any visit from Week 6 to Week 12. 					
	*No transfusion effect definition: > 1 week since last transfusion.					
To evaluate the safety of INCB050465 administered as repeat doses in participants with AIHA.	Safety and tolerability will be assessed by monitoring AEs, measuring vital signs and ECGs, and conducting clinical laboratory blood and urine sample assessments.					
Secondary						
To further evaluate the efficacy of INCB050465 in the treatment of participants with AIHA.	 Proportion of participants attaining a CR during postbaseline visits. 					
	Proportion of participants attaining a PR during postbaseline visits.					
	 Proportion of participants attaining a ≥ 2 g/dL increase in hemoglobin from baseline. 					
	Mean, change, and percentage change from baseline of hemoglobin.					
	Proportion of participants requiring transfusions.					
	Proportion of participants who achieve normalization of hemolytic markers. (Hemolysis markers: hemoglobin, haptoglobin, LDH, reticulocyte count, total bilirubin, and direct/indirect bilirubin.)					
	Change of daily usage of prednisone.					
	FACIT-F sub-scale assessment.					
To evaluate the PK effects of INCB050465.	PK endpoints: C _{max} , t _{max} , C _{min} , AUC _{0-t} , and CL/F.					
To evaluate the PD effects of INCB050465.	Change from baseline in PD markers: reticulocyte count, DAT for IgG and C3b, cold agglutinin levels, haptoglobin, total bilirubin, direct/indirect bilirubin, LDH, and complement assessment (CH50, C3, and C4).					

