2.2. Objectives and Endpoints

Objectives	Endpoints
Primary	

• To evaluate the efficacy of INCB050465 in the treatment of participants with AIHA.	
• Proportion of participants attaining a CR (defined as hemoglobin ≥ 12 g/dL not attributed to transfusion effect*) at any visit from Week 6 to Week 12.• Proportion of participants attaining a PR (defined as hemoglobin 10-12 g/dL or at least ≥ 2 g/dL increase from baseline not attributed to transfusion effect) at any visit from Week 6 to Week 12. 
*No transfusion effect definition: > 1 week since last transfusion.

• To evaluate the safety of INCB050465 administered as repeat doses in participants with AIHA.	
• Safety and tolerability will be assessed by monitoring AEs, measuring vital signs and ECGs, and conducting clinical laboratory blood and urine sample assessments.
Secondary	

• To further evaluate the efficacy of INCB050465 in the treatment of participants with AIHA.	
• Proportion of participants attaining a CR during postbaseline visits.• Proportion of participants attaining a PR during postbaseline visits.• Proportion of participants attaining a ≥ 2 g/dL increase in hemoglobin from baseline.• Mean, change, and percentage change from baseline of hemoglobin.• Proportion of participants requiring transfusions.• Proportion of participants who achieve normalization of hemolytic markers. (Hemolysis markers: hemoglobin, haptoglobin, LDH, reticulocyte count, total bilirubin, and direct/indirect bilirubin.)• Change of daily usage of prednisone.• FACIT-F subscale assessment.

• To evaluate the PK effects of INCB050465.	
• PK endpoints: C_{\max}, t_{\max}, C_{\min}, AUC_{0-t}, and CL/F.

Objectives	Endpoints

• To evaluate the PD effects of INCB050465.	
• Change from baseline in PD markers: reticulocyte count, DAT for IgG and C3b, cold agglutinin levels, haptoglobin, total bilirubin, direct/indirect bilirubin, LDH, and complement assessment (CH50, C3, and C4).

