4.1.4. Handling of Missing and Incomplete Data

In general, values for missing data will not be imputed unless methods for handling missing data are specified in relevant sections.

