7.4. Analysis of Secondary Efficacy Parameters

The secondary endpoints include:

1. Proportion of participants attaining a CR during postbaseline visits.
2. Proportion of participants attaining a PR during postbaseline visits.
3. Proportion of participants attaining a ≥ 2 g/dL increase in hemoglobin from baseline.
4. Mean, change, and percentage change from baseline of hemoglobin.
5. Proportion of participants requiring transfusions, defined as "Yes" if the last transfusion is within 7 days of the visit date and "No" otherwise.
6. Proportion of participants who achieve normalization of hemolytic markers (hemolysis markers: hemoglobin, haptoglobin, LDH, reticulocyte count, total bilirubin, and direct/indirect bilirubin).
7. Daily usage of prednisone.
8. FACIT-F subscale assessment.

All secondary endpoints will be summarized using descriptive statistics.

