7.7. Pharmacodynamic Analyses

Biomarkers from blood samples will be summarized using descriptive statistics by treatment group. Additionally, subgroup analysis will include participants with other baseline characteristics, including duration of autoimmune hemolytic anemia, concomitant autoimmune disease, and prior treatments.

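### Two Protocol footnotes disagree on when direct/indirect bilirubin is measured; if the reflex rule governs, its change-from-baseline summary is selected toward participants whose bilirubin stays high

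*Protocol*

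**What the plan says.** The Protocol gives two rules for the same analyte.

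- **Table 1, footnote k**, closes its list of markers with "total bilirubin and direct/indirect bilirubin are hemolytic markers will be measured". Table 1 marks the hemolysis-marker row at screening, Day 1 and Weeks 1, 2, 4, 6, 8, 10 and 12, with no condition on total bilirubin. Only the follow-up months carry a condition: "During follow-up, these hemolytic markers should be assessed if a participant becomes symptomatic or starts new treatment".
- **Table 5, footnote c**, attached to total bilirubin, reads "If total bilirubin is elevated above ULN, direct/indirect bilirubin will be measured". Neither fraction has its own entry in Table 5.

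The PD objective (Protocol 3, SAP 2.2) is change from baseline in a list that names total bilirubin and the fractions separately: "haptoglobin, total bilirubin, direct/indirect bilirubin, LDH, and complement assessment (CH50, C3, and C4". SAP 7.7 gives the method: "Biomarkers from blood samples will be summarized using descriptive statistics by treatment group". SAP 4.1.4 sets the general position that "values for missing data will not be imputed unless methods for handling missing data are specified in relevant sections". No SAP section covers a fraction that was not run because total bilirubin was normal.

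**The concern.** Under footnote c, whether the endpoint is observed depends on the outcome. When hemolysis eases and total bilirubin returns to normal, the fraction is no longer run, and that visit contributes no change value. The values that remain come from visits where bilirubin is still high. This missingness is tied to the quantity being summarized, so a mean of the available values does not estimate the mean for all treated participants.

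The stake is modest but real. A table of change in indirect bilirubin could show a smaller fall than occurred, in a study whose interim analysis is meant to support publications and a possible Phase 3 plan in CAD (SAP 10.1).

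**Working it through.** **1. The two rules.** If footnote k governs, the fractions exist at all nine scheduled occasions up to Week 12 (screening, Day 1 and seven treatment visits). If footnote c governs, they exist where total bilirubin exceeds ULN. Footnote c does not contain the word only, but its condition has no purpose if the fractions are always run. The documents do not say which rule the laboratory applies.

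**2. What footnote c does to the summary.** Let T be total bilirubin and F the fraction. The change F(visit) - F(baseline) exists only if T(baseline) > ULN and T(visit) > ULN. The larger the fall, the more likely T(visit) is at or below ULN, so large falls are the ones dropped. The eligibility criteria set no bilirubin threshold, so a participant can also start at or below ULN and have no baseline fraction.

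**3. Size.** The plan gives no figure to reproduce and no bilirubin data, so every input here is an assumption:
- Baseline total bilirubin is lognormal with median m = 1.5, 2 or 3 x ULN and log-SD 0.4.
- A share p = 20%, 40% or 60% of participants has a fall of f = 40% or 60%. The rest have a median ratio of 1. The log-SD of change is 0.2.
- There is one post-baseline visit, and 400,000 participants are simulated per setting.
- Change in total bilirubin stands in for change in the fraction. If the fraction is a constant share of the total, the observed-to-true ratio is the same.

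True mean change = m x exp(0.4²/2) x [(1 - p x f) x exp(0.2²/2) - 1] = 1.0833m x [(1 - pf) x 1.0202 - 1].
- m = 1.5, p = 0.2, f = 0.6: 1.625 x (0.88 x 1.0202 - 1) = 1.625 x (-0.1022) = -0.17.
- m = 3, p = 0.6, f = 0.4: 3.250 x (0.76 x 1.0202 - 1) = 3.250 x (-0.2247) = -0.73.

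Chance that a participant with a fall stays above ULN = Φ(ln[m(1 - f)] / √(0.4² + 0.2²)), where the denominator is 0.447.
- m = 1.5, f = 0.6: Φ(ln 0.6 / 0.447) = Φ(-1.14) = 0.13.
- m = 3, f = 0.4: Φ(ln 1.8 / 0.447) = Φ(1.31) = 0.91.

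The simulation agrees with both formulas and supplies the observed means (changes in x ULN):

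| m | p | f | Pairs observed | True mean change | Observed mean change | Share without a fall: observed (true) |
|---|---|---|---|---|---|---|
| 1.5 | 20% | 60% | 65% | -0.17 | 0.00 | 0.96 (0.80) |
| 1.5 | 60% | 60% | 39% | -0.56 | -0.24 | 0.81 (0.40) |
| 2 | 40% | 60% | 68% | -0.49 | -0.27 | 0.82 (0.60) |
| 2 | 40% | 40% | 82% | -0.31 | -0.26 | 0.68 (0.60) |
| 3 | 40% | 60% | 86% | -0.73 | -0.64 | 0.69 (0.60) |
| 3 | 60% | 40% | 94% | -0.73 | -0.73 | 0.42 (0.40) |

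Over all 18 settings, 13% to 91% of participants with a fall keep a baseline/post pair, against 78% to 99% of the others. The observed mean is closer to zero in 17 settings and equal to two decimals in one.

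**4. Missing baseline.** P(baseline ≤ ULN) = Φ(-ln m / 0.4). This is about 16% at m = 1.5, 4% at m = 2 and under 1% at m = 3. SAP 4.1.3 lets baseline reach back to screening, so the share with no baseline fraction could be smaller.

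**The case against.** The strongest reply is that footnote k may govern. Then the fractions are run at every treatment visit and nothing is lost. The Laboratory Manual, which might settle this, is not among the documents. Even under footnote c the consequence is limited. The fractions are one item in a descriptive secondary PD list, total bilirubin is already in that list without a ULN condition, all analyses are exploratory (SAP 3.2), and summaries report the number of observations (SAP 5.1). Appendix A lists no dedicated PD change table.

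Most of this stands and limits the weight of the point. It does not remove it. The conflict is in the text, sites or laboratories could apply either rule, and a falling n shows reduced coverage but not that the remaining values are selected.

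Two stronger readings are tempting, and the documents support neither.
- A reader might infer that every participant whose bilirubin normalizes drops out of the endpoint. Loss is by visit. Change values from earlier visits with elevated bilirubin are kept.
- A reader might infer that the summary would show mainly non-responders, with no change or a rise. The Protocol did tie response to the markers, "not attributed to transfusion effect* and the normalization of hemolytic markers) at any visit from Week 6 to Week 12", but SAP 7.2 now defines CR and PR by hemoglobin and transfusion timing alone, so a responder can still have bilirubin above ULN and be observed. In the six settings where 40% have no fall, their observed share was 0.42 to 0.81, a clear majority in only three. An illustration that places every responder below ULN removes them all by construction, so its near-zero result restates the assumption.

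**Conclusion.** The point holds conditionally. The two footnotes conflict. If footnote c governs, the change-from-baseline summary of direct/indirect bilirubin is selected toward participants with persistent bilirubin elevation and tends to understate a fall. The direction follows from the measurement rule together with the absence of imputation. The size cannot be fixed from the documents: it is negligible when baseline is well above ULN and falls are moderate, and nearly complete when baseline is close to ULN and falls are deep.

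The effect is confined to the fractions. Change in total bilirubin, LDH, haptoglobin, reticulocytes and the other PD markers is untouched, as are the primary endpoints as the SAP defines them. The secondary marker-normalization endpoint (SAP 7.4) also names the fractions and has no rule for one left unmeasured. That is a definitional gap and does not enter the sizes given here.

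**What to change.** Reconcile Table 1 footnote k with Table 5 footnote c so that direct/indirect bilirubin is reported from the existing sample at every protocol visit where total bilirubin is measured. The cost is one extra analyte on blood already drawn.

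For data already collected under reflex testing, add a line to SAP 7.7: change in total bilirubin is the bilirubin PD summary, and the fractions are listed with n per visit, without a summary of their mean change. The cost is the loss of a separate fraction summary. Total bilirubin is already a planned PD item, so no new analysis is needed.

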8.4. Pharmacokinetic Assessments

8.4.1. Blood Sample Collection

Pharmacokinetic samples will be obtained at the visits and collection times shown (see Table 6) for all participants receiving INCB050465.

The exact date and time of the PK blood draws, the date and time of the last dose of study drug preceding the blood draw (if applicable), and the time of the previous meal will be recorded in the eCRF.

Instructions for sample preparation and shipping will be provided in the Laboratory Manual. Participants will receive reminder cards in advance of the study visit providing instruction to hold the dose of study drug on the day of the visit and a place to record the time of the prior dose of study drug and time of the most recent meal or snack consumed.

Pharmacokinetic sampling will occur on 4 separate days. If the PK plasma sample collection is missed for a visit, then the sample collection should be performed at the next visit. On the PK visit days, participants must refrain from taking study drug before arriving at the research unit. Participants should not have consumed any food within 4 hours before arriving at the research unit. A predose (trough) PK sample should be collected at each of the PK visits. Following collection of the predose PK sample, INCB050465 will be administered, and subsequent timed samples will be collected (see Table 6). The participants may have a light meal following the 1 hour postdose PK sampling at Weeks 2 and 8.

Table 6: Sample Collection Time Windows for Pharmacokinetic Assessments for INCB050465

	Timing of Sample Relative to Study Drug			
Study Visit	Predose	1 h ± 10 min	2 h ± 10 min	4 h ± 30 min
Week 1	X			
Week 2 ^a	X	X	X	X
Week 8 ^a	X	X	X	X
Week 12	X			

Note: In case of dose interruption, the new timing of PK sampling should be discussed with sponsor.

^a No food intake 4 hours predose and 1 hour postdose on Weeks 2 and 8. The participants may have a light meal following the 1 hour postdose PK sampling at Weeks 2 and 8.

8.6. Unscheduled Visits

Unscheduled visits may be held at any time at the investigator's discretion, and appropriate clinical and laboratory measurements performed based on AEs or other findings.

8.7. End of Treatment

When the participant permanently discontinues study drug, then the EOT visit should be conducted. If the EOT visit coincides with a regular study visit, the EOT evaluations will supersede those of that scheduled visit, and the data should be entered in the EOT visit in the eCRF. The participant should be encouraged to return for the safety follow-up visits.

8.8. Extension Period

In the extension period of the study, participants will be required to visit the clinic per standard of care but no less frequently than every 8 to 12 weeks for dispensing of study drug (see Table 2). Safety assessments (including laboratory analytes) that are consistent with the standard of care for the participant's condition should be performed per the investigator's discretion using a local laboratory (see Section 8.3.5). All SAEs, AEs leading to treatment discontinuation, and TEAEs will continue to be collected by the sponsor. Disease status will continue to be monitored by laboratory tests including hematology panels and hemolysis markers as appropriate at a frequency consistent with the standard of care for the participant's disease.

8.9. Follow-Up

8.9.1. Safety Follow-Up

For participants who do not enter extension period, the safety follow-up period is the interval between the EOT visit (Week 12) and the scheduled follow-up visits, which should occur 30 to 35 days after the EOT visit (or after the last dose of study drug if the EOT visit was not performed). Adverse events and SAEs must be reported up until at least 30 days after the last dose of study drug, the date of the follow-up visits, or until toxicities resolve, return to baseline, or are deemed irreversible, whichever is longer. Reasonable efforts should be made to have the participant return for the follow-up visits and report any AEs that may occur during this period. If the participant cannot return to the site for the safety follow-up visits, the participant should be contacted by telephone for assessment of AEs and SAEs. Sites should be instructed to document this contact in the source.

8.9.2. Additional Follow-Up Period

Participants will have additional follow-up assessments for 12 weeks (3 months) after EOT. Safety follow-up is included in this 12-week (3 months) additional follow-up period. The following information will be collected:

- The start date of new AIHA therapy.
- Type of therapy.
- Marker for hemolysis.

If the participant withdraws consent for study drug but continues in the follow-up period of the study, the above information will also be collected.

The site will also use continuing participant records to supply data on subsequent treatment regimens and disease activities in the eCRF.

For participants who receive study drug in the extension period, the safety follow-up is included in the 12-week (3-month) additional follow-up period and should occur 30 to 35 days after the last dose of study drug.

9. ADVERSE EVENTS: DEFINITIONS AND PROCEDURES FOR RECORDING, EVALUATING, FOLLOW-UP, AND REPORTING

